#### **6.3.2.4 Vital Signs Data**

The analysis of vital signs will focus on the incidence of clinically relevant abnormalities. The number of subjects evaluated and the number and percentage of subjects with clinically relevant post-baseline abnormalities will be presented. The criteria for clinically relevant post-baseline abnormalities are shown in the following table (Table 2). Summary statistics for actual values and change from baseline will also be presented.

**Table 2 Criteria to Determine Clinically Relevant Abnormalities in Vital Signs**

Vital Sign	Criteria for Abnormalities
Temperature	>38°C or an increase from baseline of at least 1°C
Pulse	>120 beats per minute (bpm) or an increase from baseline of >20 bpm <50 bpm or a decrease from baseline of >20 bpm
Systolic Blood Pressure	>180 mmHg or an increase from baseline of >40 mmHg <90 mmHg or a decrease from baseline of >30 mmHg
Diastolic Blood Pressure	>105 mmHg or an increase from baseline of >30 mmHg <50 mmHg or a decrease from baseline of >20 mmHg

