5.5. Rationale for Dosing Regimen

The BG00012 dosage selected for this study (240 mg BID) is the approved BG00012 dosing regimen in adult patients with MS.

In adults, after oral administration, DMF is well absorbed and extensively metabolized by esterases to its primary active metabolite, monomethyl fumarate (MMF). As a result, DMF is not quantifiable in plasma, and all PK analyses have been performed based on MMF concentrations. Downstream metabolism of DMF/MMF occurs through the tricarboxylic acid cycle, with exhalation of carbon dioxide serving as a major route of elimination. The PK of BG00012 has been thoroughly evaluated in adults. Body weight is a significant covariant for BG00012 exposure in that the area under the curve and the maximum concentration are decreased by 2% and 1.4%, respectively, for every 1-kg increase in body weight within the weight range of 45 to 112 kg. This translates to a 2-fold increase in exposure levels as body weight decreases from 112 to 45 kg.

Despite the effect of body weight changes on the exposure levels of BG00012, data from the pivotal Phase 3 studies suggested that the variability in exposure did not affect safety and efficacy measures in adult patients. Notably, the efficacy and tolerability profiles of BG00012 at 240 mg BID were indistinguishable from those at 240 mg TID, with a wide range of overlapping exposures between the 2 dosages.

A Phase 1 PK study (Study 109MS101) revealed no apparent differences in the kinetics of BG00012 across the age range of 21 to 51 years once the weight relationship was accounted for.

Published data [Zhu 2009] indicate that there were no notable differences in the expression and activities of esterases in juveniles (12 to 18 years old) when compared with adults. These findings suggest that the disposition of BG00012 is unlikely to change with age for the target population (10 to 18 year olds).

Taken together, these data indicate that 240 mg BID, the approved dose in adults, should be tolerable in pediatric subjects meeting the inclusion criteria for the parent study (109MS202) and the current extension study. As such, this dose was chosen for the parent and current studies.

CONFIDENTIAL

The information contained herein may not be used, disclosed, or published without the written consent of Biogen MA Inc.

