### List of Abbreviations

AE	adverse event
BID	twice daily
CDT	Clinical Development Team
CI	confidence interval
CRF	case report form
CRO	contract research organization
DMF	dimethyl fumarate
EDC	electronic data capture
GCP	Good Clinical Practice
ICF	informed consent form
ICH	International Council on Harmonisation
IFN	interferon
IgG	immunoglobulin G
IXRS	Interactive Voice/Web Response System
MCV4	meningococcal polysaccharide diphtheria conjugate vaccine (quadrivalent)
MedDRA	Medical Dictionary for Regulatory Activities
MS	multiple sclerosis
PHI	protected health information
PPSV23	23-valent pneumococcal polysaccharide vaccine
RRMS	relapsing-remitting multiple sclerosis
SAE	serious adverse event
SMT	Study Management Team
SUSAR	suspected unexpected serious adverse reaction
Td	tetanus diphtheria toxoids vaccine
US	United States
WHO	World Health Organization

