### **6.3.2.3 Clinical Laboratory Data**

The following clinical laboratory parameters are assessed per the protocol:

- Hematology: hemoglobin, hematocrit, red blood cell count, WBC count (with differential) and platelet count.
- Blood chemistry: albumin, sodium, potassium, chloride, total bilirubin, alkaline phosphatase, ALT, AST, GGT, blood urea nitrogen, creatinine, bicarbonate, calcium, magnesium, phosphate, uric acid, and glucose
- Vitamin D and PTH (Day 1 and Week 96 only)
- Urine and serum pregnancy tests

Each laboratory value for each subject will be flagged as ‘low’, ‘normal’, or ‘high’, relative to the parameter’s normal range. Each subject’s urinalysis values will be flagged as “positive”, “negative”, or if no value is available, “unknown”.

Shifts from baseline to post baseline (Week 4/early withdrawal) high/low status for all hematology and blood chemistry parameters, and shifts from baseline to high/positive status for urinalysis will be presented.

Summary statistics will also be provided for all absolute laboratory values as well as change from baseline. The summaries for laboratory data will be data from baseline to each time point, including early withdrawal. Graphs showing the mean or change from baseline values may be presented as well.

In addition to lymphocyte count data summarized at each timepoint on study treatment, lymphocyte count over time post-treatment and the time to recovery will be descriptively summarized for subjects who develop decreases in lymphocyte count (<LLN).

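### The SAP flags abnormal blood pressure with one fixed set of limits for a population targeted at 10 to 18 years: the absolute high limits have no effect at low baselines, and the absolute low limits need no minimum fall

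*SAP*

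**What the plan says.** SAP Section 6.3.2.4 makes the proportion of subjects meeting set limits the focus of the vital-sign analysis: "The criteria for clinically relevant post-baseline abnormalities are shown in the following table". That table is Table 2 of the section, not the earlier activity table with the same number. Each blood-pressure rule joins an absolute limit and a change from baseline with an or:

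- Systolic high: ">180 mmHg or an increase from baseline of >40 mmHg"
- Systolic low: "<90 mmHg or a decrease from baseline of >30 mmHg"
- Diastolic high: above 105 mmHg, or a rise of more than 30
- Diastolic low: below 50 mmHg, or a fall of more than 20

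The same rules apply to every subject. Protocol Section 5.5 gives the target population as 10 to 18 years. Protocol Section 16.5.1.3 says that clinically relevant vital-sign abnormalities will be summarized but gives no criteria, so the SAP table alone defines the term. Section 6.3.2.4 also provides summary statistics of the values and of the changes from baseline.

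**The concern.** A fixed absolute limit means different things for a 10-year-old and for an older adolescent. If the younger subjects have low usual pressures, the high limits of 180 and 105 may be out of reach while the low limits of 90 and 50 lie close to baseline. The flag rate would then depend partly on where a child's pressure usually sits, and less on whether it moved. With one arm, no control group shows the background rate of flags, so the percentage is only as informative as the limits behind it.

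The change limits have a gap of their own. Baseline is the pre-dose Day 1 value, normally the last visit of the parent study (SAP Section 6.1.1), and inclusion criterion 2 requires subjects to be on BG00012 already. A rise that occurred earlier on treatment is therefore part of baseline. Only an absolute limit could pick it up.

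**Working it through.** The plan states no figure to reproduce, so the check applies the table as written. The limits come from SAP Section 6.3.2.4, Table 2. The baselines are assumptions, because the documents give no blood-pressure data. Let B be baseline in whole mmHg.

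**High flags.** Systolic is flagged above min(180, B + 40). The two parts are equal when B + 40 = 180, that is B = 140, so the absolute limit adds something only when B is above 140. Diastolic is flagged above min(105, B + 30). The parts are equal at B = 75, so the limit of 105 adds something only when B is above 75.

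**Low flags.** Systolic is flagged below max(90, B - 30), with the parts equal at B = 120. The smallest flagged fall is therefore B - 89 for B from 90 to 120, and 31 from 120 upward. Diastolic is flagged below max(50, B - 20), with the parts equal at B = 70. The smallest flagged fall is B - 49 for B from 50 to 70, and 21 from 70 upward.

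| Measure | B | Highest reading not flagged high | Largest unflagged rise | Smallest flagged fall |
|---|---|---|---|---|
| Systolic | 95 | 135 | 40 | 6 |
| Systolic | 100 | 140 | 40 | 11 |
| Systolic | 110 | 150 | 40 | 21 |
| Systolic | 120 | 160 | 40 | 31 |
| Systolic | 150 | 180 | 30 | 31 |
| Diastolic | 55 | 85 | 30 | 6 |
| Diastolic | 60 | 90 | 30 | 11 |
| Diastolic | 70 | 100 | 30 | 21 |
| Diastolic | 80 | 105 | 25 | 21 |

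A change from 100 to 140 systolic is not flagged, and 100 to 141 is. A change from 60 to 90 diastolic is not flagged, and 60 to 91 is. A change from 92 to 89 systolic is flagged low, as is 52 to 49 diastolic. A subject at 85 systolic at baseline who stays at 85 is flagged with no fall at all.

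**Illustration on assumed figures only.** Take normally distributed systolic pressure, a between-subject SD of 10, a within-subject SD of 6 to 8, eight post-baseline readings (the count in the SAP schedule) and no true change. In a simulation of 200,000 subjects per setting, the share with at least one low systolic flag was:

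- 44.5% to 55.4% at a group mean of 100
- 14.2% to 23.2% at a mean of 110
- 2.4% to 7.0% at a mean of 120

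High flags stayed at or below 0.2%. With a true sustained rise of 20 mmHg, 5.2% to 18.1% had at least one high flag. Under these assumptions the low-flag rate mainly follows the group's usual pressure.

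**The case against.** The strongest reply is that this is a supporting table. The primary endpoint is adverse events, serious adverse events and discontinuations due to adverse events. Any unfavorable sign can be an adverse event (Protocol Section 15.1.1), and all are recorded whatever their severity or relationship (Section 15.3.1), without reference to this table. No decision rule uses the flags, and Protocol Section 5.3.1 reports no drug-related cardiovascular effects in nonclinical safety studies. This stands, and it limits the importance of the point.

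Any hard cut-off, pediatric ones included, flags small falls in subjects just above it. This also stands. What a single limit for all ages does is decide which children sit next to the cut-off.

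A reader might infer more than the text supports:

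- **Large rises generally escape.** They do not. Every rise above 40 systolic or 30 diastolic is flagged at any baseline.
- **Trivial falls are generally flagged.** This is so only near 90 systolic or 50 diastolic. From 120 or 70 upward the fall must exceed 30 or 20.
- **The vital-sign analysis consists only of these flags.** Section 6.3.2.4 also summarizes values and changes, where a general rise would show. Group means do not identify individual children, but they are a real safeguard.
- **The limits were inherited from another study.** The SAP's abbreviation list includes "23-valent pneumococcal polysaccharide vaccine", and Section 6.3.2.3 has "Shifts from baseline to post baseline (Week 4/early withdrawal) high/low status" although the schedule has no Week 4 visit. Leftovers elsewhere do not show where this table came from, and the point does not need them.

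**Conclusion.** The point holds for blood pressure, as a weakness in a supporting safety table. At systolic baselines up to 140 and diastolic baselines up to 75 the absolute high limits add nothing, and high readings are found only by a rise of more than 40 or 30 mmHg. At baselines near 90 or 50 the absolute low limits flag small falls, or none. These statements follow from the table without any assumption.

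Their practical size does rest on assumptions. At assumed baselines of 95 to 120 systolic, a high flag needs more than 135 to 160 mmHg; at assumed baselines of 55 to 75 diastolic, more than 85 to 105. The documents give neither actual baselines nor pediatric reference values. They therefore cannot show how many flags would change, or that the table misses true hypertension or over-reports true hypotension at a stated rate. The 10 to 18 year range is a target; the extension sets no age limits of its own. Pulse and temperature limits were not examined.

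**What to change.** In SAP Section 6.3.2.4, Table 2, replace the absolute blood-pressure limits with age-, sex- and height-specific limits from a pediatric reference named before the analysis. Apply them at the subject's age at each visit. Carry the last available height forward, since height is not scheduled at every visit with vital signs (Weeks 12, 36 and 84, for example). State a rule for subjects aged 18 or over. Keep the change-from-baseline criteria and the summary statistics as a second display.

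Age, sex and repeated height are already collected, so no new data are needed. The cost is choosing and citing a reference, some programming, and less direct comparability with any earlier tables that used the fixed limits. The change affects analysis flags only, not clinical management.

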#### **6.3.2.5 12-Lead ECG**

The analysis of ECG will be summarized at each timepoint, presenting only frequencies of Normal, Abnormal – no adverse event, and Abnormal – adverse event.

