**Table 2: Additional Study Activities for Study 109MS311**

Tests and Assessments	Unscheduled Relapse Assessment Visit  (within 72 hours after symptom onset)	Discontinuation/ Withdrawal Visit  (as soon as possible but no later than 4 weeks after last dose of study treatment)	Lymphocyte Follow-Up Visit 
Physical Examination	X	X	X
Body Weight	X	X	X
Height		X	
Vital Signs 	X	X	X
12-Lead ECG		X	
Hematology 	X	X	X
Blood Chemistry 	X	X	
Urine Pregnancy Test 	X	X	
Urinalysis 	X	X	
PTH and Vitamin D Levels		X	
EDSS	X	X	
Brain MRI Scan 		X 	
Relapse Assessment	X		
Concomitant Therapy and Procedures		Monitor and record throughout the study	
AE/SAE Recording		Monitor and record throughout the study	

AE = adverse event; ECG = electrocardiogram; EDSS = Expanded Disability Status Scale; LLN = lower limit of normal; MRI = magnetic resonance imaging; PTH = parathyroid hormone; SAE = serious adverse event.

 An Unscheduled Relapse Assessment Visit will be conducted within 72 hours of symptom onset of a suspected relapse (i.e., new or recurrent neurologic symptom[s]).

 Discontinuation refers to discontinuation of study treatment. Withdrawal refers to withdrawal of subjects from the study. The Discontinuation/Withdrawal Visit should be conducted as soon as possible and no later than 4 weeks after the last dose of study treatment.

 Subjects who complete, temporarily withhold, or permanently discontinue study treatment for any reason and have a lymphocyte count <LLN will continue protocol-required visits and assessments and be followed every 4 weeks for 24 weeks and then every 3 months (unless clinically indicated more often or at the Investigator's discretion) until the lymphocyte count is  $\geq$ LLN or for 52 weeks after the last dose (whichever is sooner).

 Vital signs include body temperature, pulse rate, and systolic/diastolic blood pressure measurements.

 Hematology testing must be performed every 4 weeks in subjects with lymphocyte count <LLN

 Study treatment must be temporarily withheld or permanently discontinued if any of the laboratory values meet the criteria defined in the protocol.

 For females of childbearing potential.

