### **6.1.7 Visit Windows**

If a subject withdraws after receiving at least one dose of BG00012, but prior to the Week 96 scheduled visit, data from the early withdrawal visit will be assigned as the next scheduled visit if it has occurred within a visit window. Scheduled visits have a window of  $\pm 5$  days.

If more than one observation is within the same window, data closest to the target regular scheduled visit will be used in the summary statistics. If more than one observation falls in the same distance from the target regular scheduled visit day, the later observation will be used in the summary statistics.

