#### **6.3.2.1 Definition of Baseline Value and Visit Windows**

Baseline values and visit windows for safety summaries are defined in the same way as they are for efficacy analyses (see Section 6.1.1 and 6.1.7, respectively).

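### The SAP's ECG summary has no within-subject link to baseline, so new abnormal ECGs not recorded as adverse events can be offset by resolved ones, and most early-withdrawal ECGs have no clear place in the table

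*SAP*

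**What the plan says.** The ECG plan in SAP 6.3.2.5 is one sentence: ECGs are summarised at each timepoint, "presenting only frequencies of Normal" and of two abnormal categories, one without and one with an adverse event. Protocol 14.1 lists the 12-lead ECG among the safety assessments, but Protocol 16.5 describes analyses only for adverse events, laboratory results and vital signs, so it adds nothing on ECGs.

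SAP Section 3, Table 1 schedules ECGs at Baseline, Week 96 and the Safety Follow-Up Visit. Table 2 of the same section (additional activities) adds one at the Discontinuation/Withdrawal Visit, with this timing: "The Discontinuation/Withdrawal Visit should be conducted as soon as possible and no later than 4 weeks after the last dose of study treatment".

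A safety baseline exists. SAP 6.3.2.1 states: "Baseline values and visit windows for safety summaries are defined in the same way as they are for efficacy analyses". Two neighbouring sections use it:

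- Laboratory data (6.3.2.3) get shifts from baseline, and also: "The summaries for laboratory data will be data from baseline to each time point, including early withdrawal".
- Vital signs (6.3.2.4) get the incidence of post-baseline abnormalities, and also: "Summary statistics for actual values and change from baseline will also be presented".

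For subjects who withdraw before Week 96, SAP 6.1.7 says that "data from the early withdrawal visit will be assigned as the next scheduled visit if it has occurred within a visit window". It then adds: "Scheduled visits have a window of" ±5 days. It has no rule for a withdrawal visit that falls outside every window.

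**The concern.** The study has one treatment group, so the natural reference for a later ECG is the same subject's baseline ECG. Counts at separate timepoints discard that pairing. If some ECGs normalise while others become abnormal, the percentages can stay flat and the new abnormalities go unseen. The primary objective is long-term safety, and the reader of the report would want to know how many subjects with a normal ECG at entry had an abnormal one later.

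There is a second, smaller gap. No ECG is scheduled between Day 1 and Week 96. For a subject who leaves in between, the withdrawal ECG may be the only one after baseline, and the ECG section does not say where it is counted.

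**Working it through.** The documents state no sample size (SAP Section 5) and no ECG abnormality rates, so there is no planned figure to reproduce. Two checks are possible.

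**1. What the planned table can reveal about new abnormalities**

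Let N subjects have both ECGs, with a0 abnormal at baseline and a1 abnormal later. For the illustration, take all abnormal ECGs to be in the category without an adverse event. The number newly abnormal then lies between max(0, a1 − a0) and min(a1, N − a0), and the table fixes nothing more.

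Assume N = 20 and a0 = a1 = 2.

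- Table entries: 2/20 = 10% at each time.
- Lower bound: max(0, 2 − 2) = 0.
- Upper bound: min(2, 20 − 2) = 2.
- Subjects normal at baseline: 20 − 2 = 18, so the share newly abnormal is 0/18 to 2/18, or 0% to 11.1%.

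N and the counts are assumptions. Over a range of values:

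| Assumed N | Abnormal at each time | Newly abnormal, of those normal at baseline | Share |
|---|---|---|---|
| 15 | 2 | 0 to 2 of 13 | 0% to 15.4% |
| 20 | 2 | 0 to 2 of 18 | 0% to 11.1% |
| 40 | 2 | 0 to 2 of 38 | 0% to 5.3% |
| 15 | 4 | 0 to 4 of 11 | 0% to 36.4% |
| 20 | 4 | 0 to 4 of 16 | 0% to 25.0% |
| 40 | 4 | 0 to 4 of 36 | 0% to 11.1% |

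In each row one and the same published table fits every value in the range. A shift table would give the exact number.

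**2. Where the window rule puts an early-withdrawal ECG**

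Inputs: visits at Weeks 12, 16, 24, 36, 48, 60, 64, 72, 84 and 96 (SAP Table 1) and a ±5-day window (SAP 6.1.7). Counting from baseline, Week 96 is day 96 × 7 = 672, so there are 671 days before it.

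- Week 96 window before its target day: 5 days, 5/671 = 0.7%. This is the only scheduled post-baseline ECG in the treatment period.
- The nine earlier visits, full windows: 9 × 11 = 99 days. None of these visits has a scheduled ECG.
- Inside any window: 99 + 5 = 104 days, 104/671 = 15.5%. Outside every window: 567/671 = 84.5%.
- If the next scheduled visit must lie on or after the withdrawal day, each earlier visit takes 6 days: 9 × 6 = 54, and 54 + 5 = 59 days, 59/671 = 8.8%. Unassigned: 612/671 = 91.2%.

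These are shares of calendar days, not of subjects. The documents give no distribution of withdrawal times.

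**The case against.** The strongest reply is that adverse-event reporting already does the important work. The table separates abnormal ECGs with an adverse event from those without. SAP 6.3.2.2 counts events that begin or worsen after the first extension dose, which is a within-subject comparison, and it tabulates and lists events leading to treatment discontinuation and to study withdrawal. This stands, and it limits the concern. A reader might infer that any new ECG abnormality can disappear; the documents do not support that. What can disappear is mainly the abnormal ECG without an adverse event. The SAP provides a category for exactly these, so it expects some.

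A reader might also infer that early stoppers' ECGs have no timepoint at all. That goes too far. The Discontinuation/Withdrawal Visit is itself an ECG visit and could be read as one of the timepoints, SAP 6.1.7 gives a conditional slot, and Protocol 7.2.3 encourages those who withdraw to attend Safety Follow-Up, which has an ECG. Nor does the Week 96 column describe treatment completers only, because Protocol 10.1 lets subjects who stop treatment remain in the study and continue assessments.

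Two further points stand. ECG category is not part of the primary endpoint, and Protocol 5.3.1 reports no drug-related cardiovascular effects in the nonclinical safety studies, so the stakes are modest. And a shift table has limits of its own. Subjects enter while taking BG00012 (Protocol 8.1, criterion 2), so the baseline ECG is already on treatment. A worst-value summary would mix Week 96 with a Safety Follow-Up ECG taken off study drug, possibly on commercial product (Protocol 11.6), and subjects would have unequal numbers of ECGs.

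**Conclusion.** The concern holds in a limited form and is minor. By restricting itself to counts per timepoint, the ECG section gives up the within-subject comparison that the same SAP makes for laboratory data and vital signs, and the documents give no reason for the difference. The loss falls on new abnormal ECGs not recorded as adverse events. For these the table gives only bounds: 0% to 11% of subjects normal at baseline in the example with 20 subjects, and upper ends from 5% to 36% over the assumed values shown. The bounds assume the same subjects have both ECGs; with dropouts the table says less still.

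For early withdrawal, the defensible statement is that the ECG section does not name it, and that the window rule leaves most possible withdrawal days unassigned (84.5% to 91.2%) or attaches them to visits with no scheduled ECG.

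A shift from the 109MS311 baseline would show what is new during the extension. It should not be read as showing what arose since first exposure to BG00012, because abnormalities that appeared during 109MS202 would count as present at baseline.

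**What to change.** In SAP 6.3.2.5:

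- Keep the by-timepoint frequencies, delete the word *only*, and name the Discontinuation/Withdrawal Visit as an ECG timepoint in its own right.
- Add a 3 × 3 shift table (normal; abnormal without an adverse event; abnormal with an adverse event) from the 109MS311 baseline to the end-of-treatment ECG, meaning Week 96 or the Discontinuation/Withdrawal Visit.
- Add, separately, the same table to the worst post-baseline ECG including Safety Follow-Up, so that off-study-drug ECGs are not mixed into the end-of-treatment result.
- Use as denominator the subjects with a baseline and at least one post-baseline ECG, and report how many lack an end-of-treatment ECG.
- State in a footnote that the baseline ECG was taken on BG00012, so the tables show abnormalities new during the extension.

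The cost is one extra descriptive output with two panels, from data already collected. No visit, procedure or clinical rule changes.
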